# 9.2 Safety Parameters

# 9.2.1 Safety Parameters

Safety parameters will include

- All AEs reported
- Rate of psoas impingement
- Rate of associated groin pain (derived from the 'Operative Site Other' field on the AE form)

- Radiographic stability at each postoperative visit
- Revision or removal of any study component
- Revision or removal of the Restoration® ADM Acetabular Shell and X3®
   Acetabular Insert

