In a dual mobility system the femoral head rotates within the polyethylene acetabular insert as with traditional designs, with the exception that during extended ROM, the UHMWPE insert is able to rotate within the cup. This configuration allows improved ROM before impingement. One reason for groin pain postoperatively is the conflict of the anterior rim of the acetabular cup and the ilio-psoas tendon. Tracol et al. evaluated the in vitro depth of the psoas ilio-pubic notch and developed the Restoration® ADM cup with a 3.5 mm anterior notch. The anterior cutout is designed to mitigate conflict of the anterior portion of the cup and the psoas tendon.

The polyethylene insert utilized in the Restoration® ADM X3® Acetabular System is composed of X3® sequentially annealed UHMWPE. D'Antonio et al.¹⁰ presented clinical data from 246 cases in a prospective multicenter study (Trident® X3® Acetabular Insert Study) in which all patients received X3® polyethylene inserts. The X3® inserts had a low linear wear rate of 0.008 mm/year at 5 years which represents a 58% improvement over a first-generation annealed highly cross-linked polyethylene.

Cementless acetabular components for THA became popular in the United States in the early 1980s, primarily due to poor long-term results with cemented cups. Superior radiographic performance has been reported for cementless cups as compared with cemented fixation. The design of the Restoration® ADM Acetabular Shell is based on the Trident® PSL cementless cup. The cup is manufactured from wrought cobalt chromium alloy. The acetabular shell has a CP Titanium plasma sprayed and HA coating to establish initial good fixation. HA is a naturally occurring mineral form of calcium apatite that comprises 70% of human bone. HA is currently used as a biological coating on a variety of orthopaedic implants to stimulate bone ongrowth.

HA coating has over 15 years of published clinical history of use on the femoral stem showing 95.3% survivorship. The coating is designed to provide a roughened surface texture. It is not an ingrowth surface but rather provides a surface roughness to the component.

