## Restoration®ADM X3® Acetabular System ADVERSE EVENT

| GENERAL INFORMATION                                                           |                                                                                  |                                                  |  |  |
|-------------------------------------------------------------------------------|----------------------------------------------------------------------------------|--------------------------------------------------|--|--|
| SUBJECT INITIALS:                                                             | ONSET DATE:                                                                      | SUBJECT ID:                                      |  |  |
|                                                                               |                                                                                  |                                                  |  |  |
|                                                                               | (DD-MMM-YYYY)                                                                    |                                                  |  |  |
| I. DESCRIPTION                                                                |                                                                                  | 2)                                               |  |  |
| A. OPERATIVE SITE EVENTS                                                      | heck one event in Section A or Section                                           | В)                                               |  |  |
| 
 
Acetabular Component Loosening
 
                            | Femoral Neck Crack / Fracture                                                    | 

Soft Tissue Trauma

             |  |  |
| 
 
Acetabular Insert Crack / Fracture
 
                        | Femoral Stem Crack / Fracture                                                    | 
 
Superficial Wound Infection
 
  |  |  |
| Acetabular Migration (If > 3mm)                                               | ○ Heterotopic Bone Formation (Type III / IV) ○ Tendonitis                        |                                                  |  |  |
| 

Acetabular Shell Crack / Fracture

                           | O Hip Pain                                                                       | Thigh Pain                                       |  |  |

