| Deep Joint Infection                                                          | O Iliopsoas Tendon Impingement                                                   | 

Trochanteric Bursitis

          |  |  |
| Device Allergic Reaction                                                      | 

Intra-Prosthetic Dislocation

                                   | 

Trochanteric Crack / Fracture

  |  |  |
| Femoral Bearing Head Crack / Fracture                                         | Nerve Palsy                                                                      | 

Trochanteric Non-Union

         |  |  |
| Femoral Component Loosening                                                   | Osteolysis                                                                       | 

Wound Hematoma

                 |  |  |
| Femoral Component Subsidence                                                  | Reflex Sympathetic Dystrophy (RSD)                                               | Other (Specify)                                  |  |  |
| Femoral Head Dislocation                                                      | г                                                                                | Adverse Event Code                               |  |  |
|                                                                               | Adverse Event Description                                                        |                                                  |  |  |
|                                                                               |                                                                                  |                                                  |  |  |
| B. SYSTEMIC EVENTS                                                            |                                                                                  |                                                  |  |  |
|                                                                               | O Pulmonary Embours  closkeletal (Specify) Respiratory (Specify) Thrombophlebiti | cify) Urogenital (Specify)                       |  |  |
| C. WHEN DID THE EVENT OCCUR?                                                  | ○ Pre-Op ○ Intra-Op                                                              | O Post-Op                                        |  |  |

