| II. COMPLICATION / CONCURRENT MEDICAL                                         |                                                                                  |                                                  |  |  |
| D. DESCRIBE CIRCUMSTANCES, INCLUDING I                                        |                                                                                  | IGNS, SYMPTOMS AND DISEASES.                     |  |  |
|                                                                               |                                                                                  | •                                                |  |  |
| E. DEVICE RELATED?                                                            | * If Yes or Uncertain, please explain                                            |                                                  |  |  |
|                                                                               | source documentation to the Subject                                              | t Binder.                                        |  |  |
| Yes* No Uncertain*                                                            |                                                                                  |                                                  |  |  |
| F. SERIOUSNESS Does this event meet the Resulted in inpatient hospitalization | e definition of serious? Yes* N                                                  | * If Yes, check all that apply.                  |  |  |
| Resulted in prolonged existing hospitali                                      | zation * Specif                                                                  | y when Adverse Event became SERIOUS:             |  |  |
| Resulted in persistent or significant disa                                    | If Serious da                                                                    | ate is the same as Onset date, enter Onset date. |  |  |
|                                                                               | body function or permanent damage to a                                           |                                                  |  |  |
| body structure                                                                | ention to preclude permanent impairment o                                        | (DD-MMM-YYYY)
Df a                            |  |  |

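### The associated groin pain rate in Section 9.2.1 is drawn from one AE field only, so groin pain filed under another box is missed, and its link to psoas impingement is never defined

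*Combined protocol and SAP*

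**What the plan says.** Section 9.2.1 lists the psoas impingement rate and, as a separate parameter, the "Rate of associated groin pain (derived from the 'Operative Site Other' field on the AE form"). Section 9.2.2 promises AE rates with 95% confidence intervals but adds no derivation rule for either.

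The AE form in Appendix F allows one event per form. Its instruction, clipped at both ends in the available text, reads "heck one event in Section A or Section". The operative-site list includes Hip Pain, "Iliopsoas Tendon Impingement" and "Other (Specify"), with no box for groin pain. The form also has a field headed "Adverse Event Description" and a free-text item that starts "DESCRIBE CIRCUMSTANCES, INCLUDING" and ends "SYMPTOMS AND DISEASES".

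Section 8.1 (Adverse Event Reporting Period) has clearly related signs and symptoms recorded in the source document and grouped under a single diagnosis where appropriate. The synopsis and Section 2.1.2 pair the groin pain with psoas impingement, and Section 2.1.2 has both compared with published results.

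**The concern.** A rate is only as complete as the records it reads. This one reads a single field, on a form where the same complaint can be filed under at least two other boxes or written as a symptom of another event. The records most likely to be skipped are those where the investigator identified impingement and treated groin pain as part of it, which is the pain the parameter is named for.

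The rule also gives no test of association. Section 1.1 says "One reason for groin pain postoperatively is the conflict of the anterior rim of the acetabular cup and the ilio-psoas tendon", which leaves room for other causes. A groin-pain entry under Other could have any of them.

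The stake is modest but specific to this device. According to Section 1.1, the anterior cut-out of the shell is there to reduce conflict with the psoas tendon, and the groin-pain rate is one of two parameters that bear on that feature. An incomplete count would favour the design in the literature comparison, while an unlinked count would blur it.

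**Working it through.** The plan states no groin-pain rate and sets no sample size, test or margin for it, so there is no figure to reproduce. The check sets the rule against the form and the recording instructions.

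1. **Source of the rate.** Section 9.2.1 names the operative-site Other field and nothing else. Section 9.2.2 does not widen it.
2. **Where groin pain can be recorded.** With one event per form and no groin-pain box, a site can (a) specify groin pain under Other, (b) check Hip Pain and mention the groin in the text, or (c) check Iliopsoas Tendon Impingement and give groin pain as a symptom in the circumstances item. The rule reads (a) and does not read (b) or (c). Tendonitis, Thigh Pain and Soft Tissue Trauma are further boxes whose text could mention the groin.
3. **Whether route (c) is realistic.** The grouping instruction in Section 8.1 points towards it: impingement is the diagnosis and groin pain its symptom. Section IV of the Post-op Functional Evaluation asks for an AE form for each protocol-defined event, but a symptom grouped under a diagnosis need not be a separate event. The grouping instruction concerns the source document and leaves room for judgement, so route (c) is plausible, not certain.
4. **Link to impingement.** No section says how an Other entry for groin pain is tied to an impingement event. The extracted AE form shows no cross-reference field. Section 1.1 treats psoas conflict as one cause among several.
5. **Direction.** Steps 2 and 3 can only lower the rate, by omitting cases. Step 4 can only raise it, by counting unrelated groin pain. In symbols, net error = (unlinked Other cases − omitted cases) / N, where N is the safety population. The documents give neither count. N is also unknown in advance, because Sections 9.4.4.2 and 9.4.4.4 remove cases with outcome-relevant protocol deviations. Neither the sign nor the size can be computed.

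**The case against.** The best defence is that the rule follows the form. Impingement and hip pain have their own boxes and groin pain has none, so Other is the natural place for it. Section 9.2.2 tabulates every AE by event, so nothing disappears from safety reporting, and a case of impingement with groin pain still appears under impingement. Sites may file a separate form for each event. Section 11.4 refers to an eCRF guide supplied separately, which might tell sites to enter groin pain under Other. Appendix F is listed as draft, and the form carries an AE code field whose use is not explained.

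Much of this stands as a limit on certainty. It does not repair the rule. A tabulated row for hip pain or impingement does not show how many of those cases had groin pain, and Section 9.2.1 cites neither the guide nor the code field.

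Three stronger readings are tempting. A reader might infer that every Other entry counts as groin pain. The parameter is worded as associated groin pain, so only groin-pain entries are candidates, and what is missing is a way to apply the word associated. A reader might infer that the rate must be too low. The unlinked entries work in the opposite direction, and how sites will complete the form is unknown. A reader might also infer that safety events are lost. They are not, because all reported AEs are still listed and tabulated.

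**Conclusion.** The point holds as a minor one. As written, Section 9.2.1 gives a rate that omits groin pain recorded only under another operative-site box and counts groin pain under Other without any stated tie to impingement. This is a fault in a stated rule and not just missing detail, because following the rule exactly can give a rate that does not match its name.

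The size and net direction cannot be derived. The conclusion assumes that the AE form in Appendix F is the one used and that the separate eCRF guide, which is not available here, contains no convention that closes the gap. If the guide does direct groin pain to Other, the omission half largely falls away and the undefined link remains.

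Only this descriptive safety rate and its literature comparison under Section 2.1.2 are affected. The dislocation endpoint, the sample size, the impingement rate and the general AE tabulation are not.

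**What to change.** In Section 9.2.1, replace the parenthesis after the groin-pain parameter with wording such as:

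> Groin pain is identified from the description and circumstances text of all operative-site AE records, whichever box is checked, using a term list fixed before the text is reviewed and a manual check for negated mentions. Each case is counted once, with the safety population as denominator. The rate is reported overall, and separately for cases with and without an Iliopsoas Tendon Impingement AE in the same hip. Both onset dates are listed so that the link can be judged. The count from the Other field alone is shown alongside.

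Reading every operative-site box avoids swapping one narrow source for a slightly wider one. Listing onset dates avoids an arbitrary time window, for which the documents give no basis. Showing the Other-only count keeps the planned result visible. If the eCRF guide already holds a convention for groin pain, Section 9.2.1 should cite it.

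The cost is a change of wording and a small amount of text coding. The description, circumstances and onset-date fields are already on the form, so no new data collection is needed. The result will still depend on what sites wrote.

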### 9.2.2 Safety Analysis

All AEs will be listed, tabulated and summarized by event, number and percent of cases/subjects. AE rates and 95% confidence intervals will be presented.

For categorical variables, such as radiographic stability, the number and percent in each category will be presented.

The Kaplan-Meier survival curve of revision/removal of any study component and the Restoration® ADM Acetabular Shell and X3® Acetabular Insert will also be displayed.

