#### Secondary:

- The Kaplan-Meier survival curve of revision/removal for the Restoration® ADM X3® Acetabular System (acetabular shell and insert) will be displayed.
- A paired t-test will evaluate the changes in clinical and patient outcomes (HHS, SF-12, EQ-5D, and LEAS), preoperative to 5 years postoperative within the Restoration® ADM X3® Acetabular System (acetabular shell and insert) group, when data is available. In addition, the mean scores (HHS, SF-12, EQ-5D, and LEAS) over time will be tabulated, with standard deviation and 95% confidence intervals presented, if applicable.
- The AE rates and radiographic data will be listed and tabulated at 10 years postoperative for the Restoration®
   ADM X3® Acetabular System group, with 95% confidence intervals presented, if applicable.

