# 2.2 Safety

All operative site events as well as all serious adverse events (SAEs), excluding elective procedures, will be collected and compared to published data. It is expected that the AE rates reported for the Restoration® ADM X3® Acetabular System will be comparable to those reported in the literature for other primary THR systems and similar dual mobility cups on the market. Details regarding AE definitions, recording and reporting are in Section 8 of this protocol, Adverse Events.

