### 9.4.2 Sample Size Calculation

A literature review shows that at 10 years of follow-up there is an approximate 97% success rate using postoperative femoral head dislocation as the defining factor. Using a base success rate of 97% from the literature and a delta of 3.5%, it was calculated that 274 total cases would be needed to prove non-inferiority with 95% confidence. With a minimum of 274 cases analyzed, the primary hypothesis of the study will be met if the lower bound of the one-sided 95% confidence interval for the 10-year success rate is greater than 93.5%. By factoring in a 20% lost to follow-up rate within a 10-year period, the required enrollment increases to 343 cases. A total of 350 cases will be enrolled into the study.

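### Section 9.2.2 plans 10-year adverse event percentages without allowing for unequal follow-up or defining the denominator, although 20% loss is planned

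*Combined protocol and SAP*

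**What the plan says.** - **Summary method.** Section 9.2.2 states that "All AEs will be listed, tabulated and summarized by event, number and percent of cases/subjects", and then that "AE rates and 95% confidence intervals will be presented". Neither the rate nor its denominator is defined.
- **Horizon.** The synopsis, under the secondary statistical methods, says that "The AE rates and radiographic data will be listed and tabulated at 10 years postoperative", with 95% intervals where applicable.
- **Use.** Section 2.2 says that operative-site events and serious adverse events "will be collected and compared to published data" and expects comparable rates. Section 12.3 repeats the comparison for complications, and section 2.1.2 names psoas impingement and the associated groin pain for it.
- **Population.** Section 9.4.4.2 defines the safety population as the non-censored subjects who received the shell and insert. Section 9.4.4.4 shows that censored here means removed because of a protocol deviation that could affect outcome. It does not refer to incomplete follow-up.
- **Follow-up.** Section 9.4.2 allows for a "20% lost to follow-up rate within a 10-year period". Section 10.3 also ends follow-up at death, voluntary withdrawal, closure of a centre, or revision or removal of the study device.
- **Time-to-event methods.** Kaplan-Meier curves are specified for dislocation (9.1.4) and for revision or removal (9.2.2). No such method is named for any other adverse event.

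**The concern.** A percentage offered as a 10-year rate has a plain meaning only if everyone in the denominator was followed for 10 years or had the event first. With planned loss, that condition fails. A case lost in year 3 can contribute an event only up to year 3. Keep it in the denominator and it counts as event-free to year 10, so the percentage falls as follow-up worsens. Drop it unless it had an event, and the error runs the other way. The 95% interval corrects neither, because it describes sampling error around whichever quantity is being estimated.

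The protocol already plans time-to-event curves for dislocation and revision, so the gap concerns the remaining events that it intends to set against the literature, such as psoas impingement, groin pain, deep infection and component loosening. Late events matter most here. Section 12.2 expects late loosening and osteolysis, which are the sort of event that long follow-up can show and that loss hides most.

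**Working it through.** **Planned loss.** The protocol's own figure reproduces. Section 9.4.2 says "it was calculated that 274 total cases would be needed to prove non-inferiority with 95% confidence", and 274 / (1 − 0.20) = 342.5, which rounds up to the 343 stated; 350 are to be enrolled. So 20% loss by year 10 is the planning value used below. The documents give no timing of losses or of events. All timings below are assumptions, and loss is assumed unrelated to event risk.

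**Reading A: all implanted cases in the denominator.** Let E(t) be the share of 10-year events that have occurred by year t, and L(t) the cumulative loss, reaching 0.20 at year 10. Then

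crude percentage / true 10-year risk = ∫ [1 − L(t)] dE(t).

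*Constant hazard, even loss.* For a true 10-year risk I, put λ = −ln(1 − I)/10. A case lost at a time uniform on 0 to 10 years has an average observed risk of 1 − I/(10λ). Hence crude = 0.80·I + 0.20·[1 − I/(10λ)].

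- I = 10%: 10λ = 0.10536, the average observed risk among lost cases is 0.0509, and crude = 0.0800 + 0.0102 = 0.0902. Relative understatement is 9.8%.
- I = 3%: 10λ = 0.03046, the average is 0.0151, and crude = 0.0240 + 0.0030 = 0.0270. Relative understatement is 9.9%.

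*Other timings, total loss held at 20%:*

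| Timing of events | Even loss | Across the other loss timings tried |
|---|---|---|
| All in first 3 months | 0.2% | 0% to 2.5% |
| All in year 1 | 1.0% | 0% to 10% |
| Half in year 1, rest even | 6.0% | 2.8% to 15.0% |
| Constant hazard (I = 3%) | 9.9% | 4.9% (all loss in years 5–10) to 19.0% (all loss in year 1) |
| All in years 5–10 | 15.0% | 10% to 20% |

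Entries are relative understatement. The ceiling is 20%, reached when every loss comes before any event: 1 − 0.80 = 0.20.

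**Reading B: only cases with an event or complete 10-year follow-up.** With I = 3%, constant hazard and even loss, observed events are 0.0270 of implanted cases and event-free completers are 0.97 × 0.80 = 0.7760. The percentage is 0.0270 / (0.0270 + 0.7760) = 3.36%, a relative overstatement of 12% (3.36/3.00 = 1.12).

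**Scale against sampling error.** Taking 350 cases as the denominator (an assumption, since the safety population may be smaller), a displayed 2.70% has an exact 95% interval of about 1.3% to 5.0%. A displayed 9.02% has about 6.2% to 12.5%. The shifts of 0.3 and 1.0 percentage points lie well inside these.

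**The case against.** Number-and-percent tables are a common convention for adverse events, and these are descriptive: no margin, test or decision depends on them. Kaplan-Meier curves already cover dislocation and revision, so loosening or deep infection that leads to revision is partly captured. Several complications are early (the labelling in Appendix C lists infection, haematoma and nerve damage among intraoperative and early postoperative complications), and for those the bias is close to nil unless loss is just as early. If the published rates are themselves crude percentages with similar loss, much of the bias cancels, and replacing crude rates would create a mismatch. All of this stands and limits the effect. It does not supply a method for the remaining events. Section 9.4.1 says that a survival analysis will be done but ties it to no adverse event.

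Three stronger readings are tempting, and the documents do not support them.

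- A reader might infer that the percentages are taken over enrolled cases. The safety population is implanted, non-censored cases, and the treatment of lost cases within it is not stated.
- A reader might infer a shortfall of a tenth or more as a general rule. About 10% needs a constant hazard and even loss; with even loss, early events fall far below it. Loss above 20% has no source in the documents. Deaths and shell or insert removals cannot simply be added to the loss either: where they are competing events, those cases properly stay in the denominator.
- A reader might infer that the device will look safer than it is. Under Reading B the sign reverses, and the comparison depends on published methods that the documents do not describe.

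**Conclusion.** The point holds as a minor one. Apart from dislocation and revision or removal, adverse events are planned as simple 10-year percentages with no method for unequal follow-up and no stated rule for lost cases. Under both denominators examined the percentage misses the 10-year risk, in opposite directions. Counting all implanted cases, the relative understatement at 20% loss runs from near 0% (early events) through about 10% (constant hazard, even loss) to at most 20% (late events or early loss). Counting only cases with an event or complete follow-up, a true 3.0% would show as about 3.4%.

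These sizes rest on the planned 20%, on assumed timings and on uninformative loss. Whether the 20% already includes deaths and other terminations is not stated. The net distortion against published rates cannot be sized from the documents.

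**What to change.** In section 9.2.2:

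1. State the denominator for adverse event percentages, including whether cases lost to follow-up remain in it.
2. For the events compared with the literature (psoas impingement, groin pain, deep infection, component loosening), add cumulative incidence by the Aalen-Johansen method at 1, 2, 5 and 10 years, with 95% confidence intervals, in the safety population. Treat death and shell or insert removal as competing events.
3. Censor lost cases at last contact. Section 10.3 dates a lost case at the sponsor's approval of termination, which may come later and would add time in which nobody was observing the case.
4. Keep the crude counts and percentages alongside, for like-for-like comparison where a published rate is crude.

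The data are already planned: the adverse event form records onset date, the visit forms and questionnaires carry dates, and the termination form records the date and reason. The cost is a few extra tables and, if all implanted cases would otherwise be the denominator, slightly less favourable rates.
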